5.10 Early Termination

Procedures for Early Termination Telehealth Visits

If a subject decides to withdraw from the study prior to completion or if they are withdrawn by the Project Leader due to safety concerns, they will be scheduled for an early termination visit. If the participant is contacted within the window of a regularly scheduled visit, all measures for that visit will be collected. If the early termination visit occurs at Weeks 1, 2, 4 or 5, additional safety measures will be obtained since these measures are not scheduled at those visits. If the subject is seen outside the regularly scheduled visit window, safety measures will be obtained.

A. Physiological Measures:

- 1) Vital signs (blood pressure & heart rate) will be obtained while conducting the telehealth visit.
- 2) Carbon monoxide level will be obtained while conducting the telehealth visit.
- 3) Biomarker collection (first void or spot urine and saliva) collected prior to or at the telehealth visit and then dropped off at the brief clinic or curbside visit.

B. Surveys – *link sent to participant to complete REDCap based survey:*

The following additional assessments will be completed at early termination via REDCap, if not part of the usual measures scheduled for the regularly scheduled visit:

Subjective Outcome Measures:

- 1) Respiratory Symptoms and Global Health Questionnaire
- 2) Perceived Health Risk
- 3) Modified Cigarette Evaluation Scale – Study cigarette
- 4) Cigarette Purchase Task – Study Cigarette
- 5) Nicotine Dependence Questionnaire
- 6) Duke Sensory Questionnaire - Study Cigarette
- 7) Tobacco Policy Support Questionnaire
- 8) End of Study and Feasibility Questionnaire

C. Interviews - Research Assistant interviews participant and enters directly into REDCap:

- 1) COVID-19 Assessment
- 2) Health Changes and Menstrual Cycle Questionnaire
- 3) Adverse Event
- 4) Concomitant Medications
- 5) Daily ITR Review (follow-up on missing and unusual reports)
- 6) Timeline Follow-back Questionnaire
- 7) Intention to Quit
- 8) Product Accountability Log
- 9) Smoking Cessation Counseling
- 10) End of Visit Evaluation

5.11 Study Completion:

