- 2) Medication changes: If a participant begins taking any of the exclusionary medications or other medications that could potentially have a smoking-drug interaction post-enrollment, the medical professional will determine how best to monitor and minimize potential risks (including withdrawal if warranted). We will provide a letter to the participant that can be given to the prescribing physician and that lists potential medications that can be affected by changes in smoking that could occur as a result of participation in the study.
- 3) Any hospitalization or debilitation in which participation in the study could be detrimental to the recovery process. This will be self-reported by the participant and will be reviewed by the site PI and medical professional to determine whether continued participation in the study is appropriate.
- 4) If a participant is behaving in an inappropriate or threatening manner, admits to lying about eligibility criteria, including omitting previous medical diagnoses and medications, is participating in other smoking research studies that could affect the primary outcome measures, does not follow study instructions, etc., then the PI can withdraw him/her from the study at the PI's discretion.

- 5) If there is reason to believe the participant is sharing large quantities of the study cigarettes with other people.

Withdrawal Procedures

If the decision to withdraw a subject occurs at a study visit, regular procedures will be conducted as well as the additional early termination procedures described in 6.7. If it is determined via a phone call that withdrawal is appropriate or if the subject is dropping out, we will ask the subject to attend an exit telehealth visit to complete questionnaires, product accountability and safety assessments and to receive their final study payment.

If the subject refuses an exit visit, we will request that at the minimum, product accountability be completed. We will also stress the importance of being able to assess safety measures for the subject's safety.

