10.1 Trial Endpoints

Primary Endpoint:

- The change in total NNAL from visit 00 to week 6 visit.
- The mean CPD based on 7-day IVR data between week 00 and Week 6 visit

Secondary Endpoint:

- Change in TNE, CEMA, and PheT from visit 00 to week 6 visit
- Change in intensity of smoking measured by filter analysis collected at 00, Week 3 and Week 6.
- Change in parameters of inhalation depth measured at 00 and Week 6.
- Change in subjective measures (dependence as measured by the FTND, mCES, and Perceived Health Risk) from visit 00 to Week 6 visit.

Exploratory Endpoints:

- Change in biomarkers of other volatile organic compounds (e.g.,3-HPMA, HMPMA) from visit 00 to Week 6 visit.
- Determine concordance in biomarkers of exposure across different sample collection methods.

Secondary Endpoint

Safety Endpoints:

- Adverse Events (AEs)

- Serious adverse events (SAEs)

Randomization

Subjects will be randomly assigned using a stratified (by site), block randomization scheme into the following groups: (1) ventilated filter cigarettes; or (2) unventilated filter cigarettes.

Sample size and power considerations

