To determine the sample size for a test of non-inferiority for unventilated filter cigarettes compared to ventilated filter cigarettes (control group), we used pilot data from our original ventilated/unventilated study 1 ([name], personal communication). For the purposes of sample size considerations, we will focus on total NNAL as one of the primary outcomes. Seventy subjects had a baseline NNAL value while smoking their usual brand and 19 and 16 subjects had an end of study NNAL value for the ventilated and unventilated groups, respectively. The endpoint of interest is the change in NNAL from baseline. To normalize the distribution of NNAL, the calculations were performed in the log scale. The non-inferiority margin (NIM) was set at a 15% change between groups. This criterion was chosen because it is close to, but not greater than the upper limit of the 95% confidence interval (CI) for the geometric mean of the change in NNAL. Therefore, 73 subjects per group will achieve 80% power to detect non-inferiority for the mean change in NNAL using a one-sided, two sample t-test with a significance level of 0.05. Furthermore, with these sample sizes, a one-sided, two-sample t-test for the mean difference in cigarettes per day (CPD) from baseline will have 90% power to determine non-inferiority with a significance level of 0.05 if the NIM is 2 cigarettes. A mean difference between ventilation groups of less than 2 cigarettes is considered to be in the range of equivalence. To accommodate a 10% loss-to-follow-up rate, we plan to enroll 81 subjects per group for a total of 162.

Study Populations

Intent-to-treat

The first analysis of all primary and secondary endpoints will adhere to the intent-to-treat principle. Under this principle, all subjects randomized to one of the two study arms will be included in the analysis in the group to which they were randomized regardless of protocol violations and compliance to treatment assignment.

Per-Protocol

A second per-protocol analysis will include only participants who complete the 6 week visit without protocol violations or non-compliance.

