10.2 Statistical analysis plan

The primary objective of the statistical analysis is to compare the effects of cigarette ventilation between two study groups: ventilated filter cigarettes and unventilated filter cigarettes. All statistical analyses will be performed using SAS version 9.4 (SAS Institute Inc., Cary NC) and a p-value less than 0.05 will be considered significant.

Describing the Study Population

Descriptive statistics will be performed for data collected on demographic characteristics, subjective measures and biomarkers at different phases and visits. Baseline data will be compared between the two ventilation groups with the two-sample t-test or the non-parametric Wilcoxon rank sum test for continuous or ordinal variables and chi-square tests for categorical variables. Biomarker data may be log transformed if necessary.

Primary Endpoint Analysis

The primary endpoints are (1) the total NNAL at the 6-week visit adjusted for NNAL at end of Phase 2 (visit 00); and (2) the mean CPD based on 7 days ITR data before week 6 visit adjusted for the mean CPD during Phase 2 (visit 00). The analysis of these two endpoints will evaluate non-inferiority of the unventilated group compared to the ventilated group.

Primary Analysis

The primary analysis will be a one-sided, two-sample t-test for non-inferiority. The null hypothesis for total NNAL (analyzed in the log scale) is that the increase from end of Phase 2 (visit 00) is 15% greater in the unventilated group compared to the ventilated group. The NNAL alternative hypothesis is that the increase from baseline (visit 00) is no higher than 15% in unventilated over ventilated groups. If the null hypothesis is rejected in favor of the alternative hypothesis, we will conclude that the unventilated filters are no more harmful in terms of NNAL exposure than the ventilated filter and may actually be less harmful. Similarly for the CPD, the non-inferiority t-test will have a null hypothesis that the 6 week mean increase in CPD from end of Phase 2 (visit 00) for the unventilated group is greater than 2.0 cigarettes compared to the ventilated group. The alternative hypothesis is that the CPD increase in the unventilated group is no more than a mean of 2.0 cigarettes verses the CPD increase in the ventilated group and the unventilated group may even smoke fewer cigarettes.

Secondary Analysis

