Every effort will be made to limit the amount of missing data in this trial. Study participants will be incentivized to attend study sessions. That said, some level of missing data is inevitable in a study of this kind. We will compare subjects who do and do not complete the study sessions in order to identify baseline covariates associated with study completion.

Our primary approach to handling missing data will be a sensitivity analysis using multiple imputation with the Markov Chain Monte Carlo (MCMC) method³⁵ carried out in PROC MI in SAS, where missing values are imputed using regression models developed from baseline covariates. Values can be imputed for both continuous and categorical variables. If the ventilation groups are associated with missing data, we will conduct multiple imputation for each ventilation group separately. Following imputation, standard statistical methods can be applied. A final single

assessment of ventilation group difference will be obtained from combining the results across the imputed datasets using PROC MIANALYZE in SAS.

Interim Analyses

No interim analysis is planned.

11 Supporting Documentation and Operational Considerations

Informed Consent Procedure and Documentation

Potential subjects will be told the nature of the research over the phone during screening and then at a virtual orientation meeting where the study is described in detail. All potential study participants will be provided a copy of the IRB-approved consent form to review prior to signing. They will be told they may discontinue participation at any time and will not be discriminated against if they choose to do so. Subjects will be told their participation in the project will be strictly confidential, that any identifying information will be available to the project investigators or institutional or federal regulatory groups only, and that no identifying information concerning the data and results will be made known. The investigator or designee will explain all aspects of the study in lay language and answer all questions regarding the study. Subjects will be required to demonstrate an understanding of the study purpose and procedures prior to signing the consent form. If the participant decides to participate in the study, he/she will be asked to sign and date the consent document and will receive a copy for their records. Consent form must be signed before the research is started.

Confidentiality of Data

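### The primary t-test has no rule for a missing Week 6 value, and the imputation, as worded, ignores leavers' Week 3 NNAL and earlier cigarette counts

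*Combined protocol and SAP*

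**What the plan says.** **Endpoints and test.** Section 10.1 defines the NNAL endpoint as "The change in total NNAL from visit 00 to week 6 visit". Section 10.2 defines the CPD endpoint as "the mean CPD based on 7 days ITR data before week 6 visit", adjusted for Phase 2. It continues: "The primary analysis will be a one-sided, two-sample t-test for non-inferiority".

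**Analysis set.** Under intent-to-treat (10.1), "all subjects randomized to one of the two study arms will be included in the analysis in the group to which they were randomized", whatever their compliance. Neither section says how a subject without a Week 6 value enters the t-test.

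**Missing data.** Section 10.2 calls multiple imputation both its primary approach and a sensitivity analysis, and says that "missing values are imputed using regression models developed from baseline covariates". Imputation is done by arm only if arm is associated with missingness.

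**Data available from leavers.** NNAL is measured at Week 3 (procedure table), and cigarettes are reported daily by text (5.4). Section 10.2 also has a supplementary mixed model of NNAL and CPD over all visits from 00.

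**Exit samples.** Section 5.10 lists "Biomarker collection (first void or spot urine and saliva) collected prior to or at the telehealth visit", and the procedure table marks urine and total NNAL at early termination. Section 9.2 has two routes. Withdrawal at a study visit brings in the early termination procedures, by reference to a section 6.7 that does not exist. After a phone decision or drop-out, "we will ask the subject to attend an exit telehealth visit to complete questionnaires, product accountability and safety assessments", with no biosample listed.

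**The concern.** A subject who leaves before Week 6 has no value for the primary t-test. With no stated rule, the software drops that subject and the test describes completers, while the plan describes everyone randomised.

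The imputation should show whether this matters, but it is built on information from before the randomised cigarettes were smoked. If some people leave the unventilated arm because their exposure rose, that rise can be seen in their Week 3 NNAL and daily counts but not in their baseline covariates. A baseline-only model gives them roughly the average change of those who stayed, so the sensitivity analysis tends to repeat the completers' answer.

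This matters more in a non-inferiority trial, because losing high-exposure subjects from the unventilated arm moves the estimate towards the conclusion the trial hopes to reach.

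**Working it through.** **1. The plan's own figures.** 10.1 gives 73 evaluable per arm, one-sided alpha 0.05, 80% power, a 15% NNAL margin, and 81 enrolled per arm for 10% loss.
- Enrolment: 73 × 1.10 = 80.3, rounded up to 81 (73 / 0.90 = 81.1 would round up to 82). The stated 81 is reproduced within rounding.
- No SD is stated. Solving backwards with a true difference of zero: SD = ln(1.15) × √(73/2) / (1.645 + 0.842) = 0.1398 × 6.042 / 2.487 = 0.340, or 0.338 with the noncentral t. I use 0.338.
- At 10% loss, 81 × 0.90 = 72.9 remain per arm, which is the number the power calculation assumes. The issue is therefore bias, not planned power.

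**2. How far leavers can move the result.** Let a fraction d leave each arm, and let the between-arm NNAL ratio among leavers be r times that among completers. The log difference for all randomised subjects then differs from the completers' by d × ln(r).
- d = 10%, r = 1.5: 0.10 × 0.405 = 0.041, a shift of 4.1%.
- Using up the whole margin at d = 10% needs r = exp(0.1398 / 0.10) = 4.05.
- For CPD, the gap among leavers would have to be 2 / 0.10 = 20 cigarettes.

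At the planned loss, the effect is a distortion of the error rate rather than a reversal of the result.

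**3. Error rate of the completers' t-test.** Simulation inputs: 81 per arm, SD 0.338, true ratio exactly 1.15, and 10% loss after Week 3. Assumed, not in the documents: correlation of Week 3 and Week 6 changes 0.5-0.7, and drop-out that depends on the Week 3 change through the stated log-odds per SD. In the one-arm cases, the ventilated arm loses subjects at random. Nominal error is 5%.
- Unventilated arm only, log-odds 0.5: completers' ratio 1.142-1.137, false non-inferiority 6.5-7.5%.
- Unventilated arm only, log-odds 1.5: ratio 1.127-1.115, about 10-14%.
- Same mechanism in both arms: ratio 1.15, about 5%.
- Direction reversed (those with smaller rises leave): ratio 1.175-1.183, about 2%.

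**4. What each imputation does.**
- *Baseline covariates, by arm.* If they do not predict the post-randomisation rise, leavers receive their arm's completer mean and the ratios in step 3 stay as they are.
- *Baseline covariates, arms pooled and arm left out of the model.* Imputed values carry no arm difference. A completers' log difference of 0.1398 becomes 0.90 × 0.1398 = 0.126, a ratio of 1.134. Arm therefore has to be in the model.
- *Week 3 NNAL added, by arm.* Under the strong one-arm mechanism, the ratio returns to 1.148-1.150. In a separate set of runs with 10-30% missing, the error rate was 4.3-6.0%.

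**The case against.** **The mixed model already uses the data.** This is the strongest point, and most of it stands. In the same scenarios, a likelihood estimate with arm-by-visit means gives 1.148-1.151, as good as the improved imputation. Section 10.2 also notes that such models can be adapted to non-inferiority. But the model is supplementary, and the only fixed effect it names is the group indicator plus unspecified predictors. Without a group-by-visit term, the group coefficient averages over visits that include visit 00, when both arms had smoked the same ventilated cigarette. It is not a Week 6 contrast to set against the margin.

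**Week 3 is not expressly excluded.** The named MCMC method imputes jointly, so a Week 3 variable would inform Week 6 if it were included. True, but the text names baseline covariates and nothing else.

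**The direction is unknown.** This stands. Section 7 anticipates irritation, nausea and cough on unventilated cigarettes, not higher NNAL among leavers. Aversion could equally reduce smoking, and 5.13 keeps abstainers on the visit schedule.

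**The repair is partly built in.** This also stands. Drop-out was generated from Week 3, so conditioning on Week 3 must work. It does nothing for people who leave earlier.

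**Exit urine is not lost wholesale.** A reader might infer that 9.2 cancels a sample that 5.10 demands. Section 9.2 is silent only on the phone or drop-out route. For a subject seen outside a visit window, 5.10 names only safety measures, and 5.8 lists exit urine only where applicable. Section 5.8 also provides a drop-off visit after each telehealth visit. These passages need reconciling; they do not show that samples will be lost.

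**Conclusion.** The primary t-test is in practice a completers' test, and the only stated missing-data method, as worded, does not use the post-randomisation data best able to show whether that matters. Both points rest on the text and need no assumption.

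The size does need assumptions: the back-solved SD, the correlation, and above all which subjects leave. At 10% loss, the false non-inferiority rate runs from about 2% to about 14% across the mechanisms tried, and a mechanism shared by both arms leaves it at about 5%. These figures show possible size and are not a forecast for this trial.

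Three stronger readings are not supported:
- That the whole intent-to-treat analysis is a completers' analysis. The imputation includes every randomised subject, and the mixed model uses intermediate visits.
- That the plan is biased towards non-inferiority. The documents do not say who will leave or why.
- That half the sample may be lost because the pilot had 70 baseline and 35 (19 + 16) end-of-study NNAL values. No reasons for the difference are given.

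A reader might also infer from the provision that if a subject "does not follow study instructions, etc., then the PI can withdraw him/her from the study", the intent-to-treat definition requires continued collection. That definition governs analysis, not collection, and this point takes no position on the withdrawal rules.

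**What to change.** 1. In 10.2 Missing Data, impute Week 6 log NNAL and CPD from arm (or separately by arm), visit 00 and Week 3 NNAL, and weekly mean CPD from the daily texts up to exit. State that this imputed analysis is how randomised subjects without a Week 6 value enter the intent-to-treat non-inferiority comparison.
2. In the 10.2 mixed model, add visit and group-by-visit terms, so that it gives a Week 6 group contrast to compare with the margin.
3. Reconcile the phone or drop-out exit visit in 9.2, and its reference to section 6.7, with 5.10, 5.8 and the procedure table.

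Exit NNAL should not be entered as a separate predictor of Week 6 NNAL. Almost nobody will have both values, so the relation cannot be estimated.

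The cost is SAP wording, a short protocol correction and slightly more analysis work, with samples and texts already scheduled. The limit is that subjects who leave before Week 3 contribute only their daily counts.

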11.1 Data and Safety Monitoring Plan (DSMP)

See the full Data and Safety Monitoring Plan document for complete information.

At each of the sites, the site PI and licensed medical professional will conduct regular conference calls or virtual meetings with the study staff to review patient's progress and their experiences with the tobacco products, including any adverse events. Entrance criteria will be reviewed following screening. Medical history will be reviewed by the medical professional for any contraindications for the use of the study cigarettes and out of range vital signs checked at each visit. Subjects will be under medical supervision while in the study and contacted on an ongoing basis by our research staff who will assess adverse events and make appropriate referrals to the medical staff. The study coordinator (with direction from the medical professional) at each of the sites will be responsible for the daily oversight of subject safety. The Data and Safety Monitoring Board (DSMB) and other regulatory bodies will be informed of any adverse events either at the regularly convened meetings or in the annual report, or if necessary, immediately.

The DSMB for this center will review the protocol and establish guidelines for data and safety monitoring. This will include developing standard procedures for day-to-day monitoring by the internal monitors, investigators and study staff. This Board will meet at regular intervals (at least once a year) to evaluate the progress of the trial, review data quality, recruitment, study retention, and examine other factors that may affect study outcome. They will also review the participants' ability to achieve the study requirements and the rates of adverse events to determine whether there has been any change in participant risk. Their review will ensure that subject risk does not outweigh the study benefits. A brief report will be generated from each of these meetings for the study record and forwarded to the Institutional Review Boards (IRB).

The DSMB will be available to convene outside of the regular meetings, if necessary, if concerns should arise regarding a particular subject, or any troublesome trends in the subject experiences. They will make appropriate recommendations for changes in protocol, if needed.

The University of Minnesota and The Ohio State University NCI designated Cancer Center also has a Cancer Protocol Review Committee that meets on a monthly basis to review all cancer-related protocols. This study will be subjected to review by this committee. Progress reports to this committee are submitted on at least a yearly basis.

All product-related adverse events of a non-serious nature will be reported to the IRB at the time of renewal. Reportable serious and related adverse events will be reported by telephone or email to the IRB within the 5 days of our receipt of information regarding the event and written reports will be submitted within 10 days. The DSMB will review all serious or unexpected adverse events and provide recommendations.

NCI will be informed of any significant action taken as a result of the DSMB's findings. Subjects will be informed of any changes in risk.

Record Retention

The investigator will retain study records including source data, copies of case report form, consent forms, HIPAA authorizations, and all study correspondence in a secured facility for at least 6 years after the study file is closed with the IRB and FDA.

12 Conduct of the Study

Good Clinical Practice

The study will be conducted in accordance with the appropriate regulatory requirements. Essential clinical documents will be maintained to demonstrate the validity of the study and the integrity of the data collected. Master files will be established at the beginning of the study, maintained for the duration of the study and retained according to the appropriate regulations.

Ethical Considerations

The study will be conducted in accordance with ethical principles founded in the Declaration of Helsinki. The IRB will review all appropriate study documentation in order to safeguard the rights, safety and well-being of the patients. The study will only be conducted at sites where IRB approval has been obtained. The protocol, consent, written information given to the patients, safety updates, annual progress reports, and any revisions to these documents will be provided to the IRB by the investigator.

Duration of Study Participation

A subjects' direct study involvement is approximately 13 weeks:

Phase 1: Baseline ~1 week;

Phase 2: Ventilated Study Cigarette - 2 weeks

Phase 3: Intervention: Unventilated or Ventilated Study Cigarette - 6 weeks

Follow-up: One visit 4 weeks post intervention.

Study sites

The sites will be University of Minnesota-Twin Cities (PI: [name]) and The Ohio State University (PI: [name])

Subject Identifier

Project and Site Identifier:

8 = University of Minnesota

9 = Ohio State University

Subject ID:

UMN: 8001 – 8350

OSU: 9001 – 9350

Data Collection Time Points Identification Numbers:

93 = Screening

92 = Phase 1: Baseline

91 = Phase 2: Ventilated study cigarettes

00 = Phase 3: Randomization to ventilated or unventilated

01 = Week 1 visit

02 = Week 2 visit

03 = Week 3 visit

04 = Week 4 visit

05 = Week 5 visit

06 = Week 6 visit - End of Intervention visit

10 = Week 10 Follow-up visit

86 = Early Termination Visit

98 = Additional Visit

Procedure Table		Platform	SCRN 93	BL-92	BL-91	BL-00	Week 1	Week 2	Week 3	Week 4	Week 5	Week 6	Follow-Up 10	Early Term
				UB	Phase 2		Phase 3 INTERVENTION							
Phone Recruitment Questionnaire	REDCap/Interview	X												
VISIT ASSESSMENTS														
Weight & height (92 only)	REDCap/Interview	X												
Vitals (blood pressure & heart rate) ¹	REDCap/Interview	X	X	X	X	X	X	X	X	X	X	X	X	X
Carbon Monoxide ¹	REDCap/Interview	X	X	X	X	X	X	X	X	X	X	X	X	X
Pregnancy Screen [hCG detection]	REDCap	X										X		
Compliance Review	Progress Note		X	X	X	X	X	X	X	X	X			
Intention to Quit	REDCap/Survey		X	X	X	X	X	X	X	X	X			X
Smoking Cessation Counseling ²	Progress Note											X	X	X
VISIT FORMS														
Concomitant Medications	REDCap/Survey	X	X	X	X	X	X	X	X	X	X	X	X	X
Health Changes Questionnaire	REDCap/Interview		X	X	X	X	X	X	X	X	X	X	X	X
Adverse Events Assessment	REDCap/Interview		X	X	X	X	X	X	X	X	X	X	X	X
Randomization	REDCap/RA				X									
Product Accountability Log	REDCap/RA			X	X	X	X	X	X	X	X	X		X
End of Visit Evaluation	REDCap/RA	X	X	X	X	X	X	X	X	X	X	X	X	X
SCREENING QUESTIONNAIRES														
Tobacco Use and Exposure History	REDCap/Interview	X												
Identifying Information	REDCap/Survey	X												
Demographics for MCC Registration	REDCap/Survey	X												
Demographics	REDCap/Survey	X												
Brief Medical History	REDCap/Survey	X												
PHQ (PrimeMD) ³	REDCap/Survey	X												
Alcohol Use Questionnaire 12 mo.	REDCap/Survey	X												
Drug Use Questionnaire 1 mo.	REDCap/Survey	X												
BIOMARKER MODIFER QUESTIONNAIRE														
Environmental Exposure Question	REDCap/Survey		X		X			X			X		X	
TOBACCO USE MEASURES														
ITR Daily Text	ITR (RC/Twilio)		X	X	X	X	X	X	X	X	X	X		X
ITR Review	ITR (RC/Twilio)		X	X	X	X	X	X	X	X	X	X	X	X
Timeline Follow-back	REDCap/Interview		X	X	X	X	X	X	X	X	X	X	X	X

Procedure Table	Platform	SCRN 93	BL-92	BL-91	BL-00	Week 1	Week 2	Week 3	Week 4	Week 5	Week 6	Follow-Up 10	Early Term	
			UB	Phase 2		Phase 3 INTERVENTION								
Tobacco Use 7 Day Followback Form		X										X		
ADVERSE CONSEQUENCES														
MNWS	REDCap/Survey		X	X	X	X	X	X	X	X	X			
QSU - Usual cigarettes	REDCap/Survey		X											
QSU - Study cigarettes	REDCap/Survey			X-V	X-V	X	X	X	X	X	X			
Respiratory Symptom Questionnaire	REDCap/Survey		X	X	X	X	X	X	X	X	X	X	X	
OTHER MEASURES														
Nicotine Dependence Questionnaire	REDCap/Survey	X-UB			X-V							X-SC	X-UB	X-SC
Contemplation Ladder	REDCap/Survey	X										X		
Covid-19 Symptom Questionnaire	REDCap/Interview	X	X	X	X	X	X	X	X	X	X	X	X	X
End of Study Questionnaire	REDCap/Survey											X		X
ACCEPTABILITY MEASURES														
Cigarette Eval. Scale Usual brand	REDCap/Survey		X											
Cigarette Eval. Scale Study cigs	REDCap/Survey			X-V	X-V	X		X				X		X
Perceived Health Risk	REDCap/Survey		X		X-V	X		X				X		X
Cigarette Purchase Task-Usual Cigs	REDCap/Survey		X											X
Cigarette Purchase Task-Study Cigs	REDCap/Survey				X-V							X		X
Duke Sensory Questionnaire	REDCap/Survey		X	X-V	X-V	X		X				X		X
Tobacco Policy Support Questionnaire	REDCap/Survey		X									X		X
OTHER														
Cigarette Butt Collection	REDCap/RA				X			X				X		
Inhalation Measures	REDCap/RA				X							X		
BIOMARKERS ⁴														
Total Nicotine Equivalents	BMW (REDCap)		X			X ⁵			X			X		X
Total NNAL	BMW (REDCap)		X			X ⁵			X			X		X
N HOCH-dAdo and N ethylidene-dGuo	BMW (REDCap)		X			X ⁵			X			X		X
Phet & 3-PheOH	BMW (REDCap)		X			X ⁵			X			X		X
Mercapturic acids ⁶	BMW (REDCap)		X			X ⁵			X			X		X
8-iso-PGF and PGE-M	BMW (REDCap)		X			X ⁵			X			X		X

Procedure Table		Platform	SCRN 93	BL-92	BL-91	BL-00	Week 1	Week 2	Week 3	Week 4	Week 5	Week 6	Follow-Up 10	Early Term
				UB	Phase 2		Phase 3 INTERVENTION						-	
Metabolomics	BMW (REDCap)			X		X ⁵			X			X		X
2 (4.5ml) Biorepository	BMW (REDCap)			X		X ⁵			X			X		X
BIOSAMPLES														
Saliva NMR	BMW (REDCap)			X										
Urine	BMW (REDCap)			X		X			X			X		X
Saliva	BMW (REDCap)			X		X			X			X		X
Buccal cells	BMW (REDCap)					X						X		
Blood Spot	BMW (REDCap)					X						X		
Hair Sample	BMW (REDCap)											X		

